#### **6.2.7. COVID-19 Impacted Visits**

A summary of the number and percentage of subjects with any visit impacted by the COVID-19 pandemic and each visit impacted by the COVID-19 pandemic may be produced. The summary will include the impact and the reason for impact overall (any visit) and at each impacted visit.

A listing of all subjects with visits and assessments impacted by the pandemic will be produced.

A figure of COVID-19 pandemic visit impacts may be produced. The figure is a stacked bar chart for each impacted visit. The stack bar is color coded by impact.

## 7. EFFICACY ANALYSES

### 7.1. Primary Efficacy Analyses

The primary efficacy estimand is the effect of daprodustat treatment relative to rhEPO on the change in Hgb from baseline to the average of all values in the EP, regardless of adherence to treatment including interruptions and discontinuations, the use of non-randomized ESA medication for any reason including rescue therapy, or the use of blood transfusions, in patients defined by the inclusion/exclusion criteria and assuming patients do not die before the end of the EP.

#### 7.1.1. Endpoint / Variables

Mean change in Hgb between baseline and over the evaluation period (EP, mean over Week 28 and 52).

#### 7.1.2. Summary Measure

Model-adjusted mean treatment difference (LS mean difference) in Hgb change between baseline and over the evaluation period.

#### 7.1.3. Population of Interest

The target population is defined by the study's inclusion and exclusion criteria.

The analysis population included in the primary efficacy analyses will be based on the All Randomized (ITT) population, unless otherwise specified.

#### 7.1.4. Strategy for Intercurrent (Post-Randomization) Events

The following are the intercurrent events for the primary efficacy analyses:

- Death prior to the end of the EP (i.e. before Week 52 visit)
- Study treatment interruption or discontinuation prior to the end of the EP
- Use of non-randomized ESA medications for any reason including rescue prior to the end of the EP
- Receipt of blood transfusions prior to the end of the EP

Except for the intercurrent event of deaths prior to the end of the EP, a treatment policy strategy will be used in which all Hgb data recorded during the EP (Weeks 28-52) will be included in the primary efficacy analysis, regardless of discontinuation or interruption of study medication due to any reasons, and regardless of receipt of non-randomized ESA medications for any reason including rescue, or blood transfusions. For deaths, a hypothetical strategy will be used as described in Section [7.1.5.1](#).

The following are causes of missing Hgb data affecting the primary efficacy endpoint that are not due to intercurrent events:

- Study withdrawal prior to the end of the EP

- Permanent switching from clinic visits to remote visits prior to end to EP
- Intermittent missing Hgb values at one or more visits with the EP

Missing data will be imputed as described in Section 7.1.5.1.

### 7.1.5. Statistical Analyses / Methods

Details of the planned displays are provided in [Appendix 10: List of Data Displays](#) and will be based on GSK data standards and statistical principles.

Unless otherwise specified, endpoint / variable defined in Section 7.1.1 will be summarised using descriptive statistics, graphically presented (where appropriate) and listed.

#### 7.1.5.1. Statistical Methodology Specification

Endpoint / Variables

 
• Mean change in Hgb between baseline and over the evaluation period (EP, mean over Weeks 28 to 52)
 

Model Specification

 
• Hgb during the EP will be defined as the mean of all available post-randomization Hgb values (on and off-treatment) during the EP (Week 28-52).
 
• The ANCOVA model used to quantify the difference in mean Hgb change will adjust for the following baseline values: 
 
○ Treatment
 
○ Baseline Hgb (see Section 5.2.1)
 
○ Region (as randomized, see Section 5.3 & Section 5.4.1)
 
 
 

Multiple Imputation Analysis

 
• Multiple imputation analysis will be performed using all available Hgb values (on and off-treatment) and conducted under a set of assumptions about missing Hgb values (see Section 14.6.3). 
 
○ Intermittent missing post-baseline scheduled Hgb data in both arms through Week 52 will be imputed using PROC MI procedure with NIMPUTE = 200 and MCMC IMPUTE = monotone to generate 200 datasets with only monotone missing patterns. Burn in iterations (NBITER) and maximum iteration (MAXITER) will both be set to 500. The seed for reproducibility is set to 204837. The imputations will be done by study treatment, and region.
 
○ For each of the monotone missing dataset (out of the 200 imputed as indicated above), the missing scheduled Hgb values through Week 52 will be imputed based on the MAR assumption and will be performed using PROC MI by treatment, and region. The monotone regression will have baseline Hgb, prior scheduled (possibly imputed) Hgb values, and may include region, as covariates (see Model Checking & Diagnostics, below). The seed for reproducibility is set to 204837.
 
○ The low and high cutoffs at Hgb values of 6 g/dL and 15 g/dL will be applied to all imputed Hgb values.
 
 
 

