5.4. Scientific Rationale for Study Design

- This study includes a Week -4 Screening Visit prior to randomization (Day 1). The screening period permits time to assess eligibility based on laboratory assessments and ultrasound evaluation.
- The total treatment period will be 52 weeks in order to allow sufficient time to demonstrate efficacy. The SP from Day 1 to Week 28 allows participants to have their study treatment dose titrated to achieve the Hgb target range. This period of time provides the best opportunity for participants to be titrated to their optimal dose of study treatment prior to the EP, from Week 28 to Week 52. A percentage of participants may still need dose titration during the EP.
- The selection of rhEPO as the active control (epoetin alfa) is based on clinical practice in the majority of participating countries.
- This study will be conducted in a double-blind fashion. Each participant will receive oral tablets (either daprodustat or matching placebo) and IV injections (either epoetin alfa or saline). Each participant will receive one active study treatment and one inactive study treatment, depending upon the treatment arm to which the participant is randomized. See [Section 7.2](#) for further information about study treatment. Because it was not feasible to create a matching placebo/saline vial for the active control (epoetin alfa), the study treatment IV injections (either epoetin alfa or saline) will be prepared and administered by an unblinded nurse, or other properly qualified individual(s), in a manner that will maintain the blind. Further information about blinding considerations are presented in [Section 7.4](#).
- Participants will be randomized in a 2:1 ratio to daprodustat or epoetin alfa. More participants will be randomized to daprodustat compared to epoetin alfa in order to obtain an adequately sized safety database of HD patients exposed to daprodustat administered three-times weekly for a longer duration (i.e., over a 52-week treatment period).

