The daprodustat starting doses and dose steps from the once daily Phase 3 study (200807) were selected based on exposure-response longitudinal modeling of Hgb data collected across the Phase 2 program and these doses serve as the foundation for the three-times weekly doses in this study. Similar to the Phase 3 study, the starting doses will be assigned based on the participant's prior dose of rhEPO or its analogs at study entry. Covariate analyses elucidated that baseline Hgb, body-weight, and prior dose of rhEPO and its analogs were the most relevant covariates of Hgb response to daprodustat. Simulations showed the effect of body-weight was not clinically important for dosing, so the relationship between prior dose of rhEPO and its analogs and response was used to determine starting doses of daprodustat relative to a participant's prior dose of rhEPO and its analogs. These findings apply to daprodustat administered three-times weekly as well, and therefore prior dose of rhEPO or its analogs will also be used in the determination of the starting dose in the current study.

The once daily doses used in the 200807 study were converted to corresponding three-times weekly doses using the estimated dose conversion ratio of approximately 2.0 that was determined in the Phase 2A three-times weekly daprodustat dose ranging study (204836). The dose conversion ratio was estimated by taking the ratio of three-times weekly daprodustat dose corresponding to the once daily dose that produced an equivalent Hgb response. Several approaches were explored to estimate the dose conversion ratio and the three-parameter Bayesian E_{max} dose-response models produced the most consistent estimates across the studied dose range. The ratio of approximately 2.0 estimated by this approach was used to calculate the three-times weekly doses.

The resultant three-times weekly starting doses of 8, 12, 16 and 24 mg were calculated by multiplying the once daily dosing algorithm by the conversion ratio estimated in study 204836. These doses are estimated to maintain equivalent Hgb concentrations to that achieved in the participants on prior rhEPO therapy and its analogs. The actual starting dose for each participant will be individualized based upon their prior therapy of rhEPO or its analogs. The highest available dose of daprodustat in the dose adjustment scheme is 48 mg administered three-times weekly.

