6.1. Inclusion Criteria

Participants are eligible to be included in the study only if all of the following criteria apply at **screening (Week -4)** and **randomization (Day 1)**, unless otherwise specified:

1. **Age:** Participant must be 18 to 99 years of age inclusive, at the time of signing the informed consent.

Note: Country-specific age requirements for Korea are provided in [Appendix 8](#), Section 12.8.2.

2. **RhEPO or its analogs:** Use of any approved rhEPO or analog for at least 8 weeks prior to the screening visit and continuing during the screening period until randomization (Day 1).
3. **Hemoglobin** concentration (measured by HemoCue) within the following range:

	Hgb Range (inclusive)
Week -4	
 • Hgb 8 to 11.5 g/dL¹ (5 to 7.1 mmol/L). • If Hgb is 11.6 to 11.9 g/dL² (7.2 to 7.4 mmol/L), up to two retests are allowed; the retest value must be between 8 to 11.5 g/dL¹ (5 to 7.1 mmol/L).
Day 1	
 • Hgb 8 to 11 g/dL¹ (5 to 6.8 mmol/L) and receiving at least the minimum rhEPO or analog dose³. • Hgb >11 to 11.5 g/dL¹ (6.8 to 7.1 mmol/L) and receiving greater than the minimum rhEPO or analog dose³.

1. Conversion from g/dL to g/L is 1:10, e.g., Hgb of 8 to 10 g/dL is equivalent to 80 to 100 g/L.
2. The first retest will use the original Week -4 blood sample. If the retest value is >11.5 g/dL, one additional retest can be performed using a new blood sample on the study visit day. The **final** retest value is entered into the IRT system. Retests will be done prior to dialysis.
3. **Minimum rhEPO or analog dose:** Epoetins (including biosimilars): 1500 units (U)/week intravenous (IV) or 1000 U/week subcutaneous (SC); Darbepoetin alfa: 20 µg/4 weeks SC/IV; Methoxy PEG-Epoetin: 30 µg/month SC/IV.

4. **Dialysis:** On hemodialysis (including hemofiltration or hemodiafiltration) >90 days prior to screening and continuing during the screening period.
5. **Frequency of Dialysis:** On hemodialysis (in-center) ≥ 3 times per week.
6. **Sex:** Male and female participants are eligible. A female participant is eligible to participate if she is not pregnant (see [Appendix 4](#)), not breastfeeding, and at least one of the following conditions applies:
 - Not a woman of childbearing potential (WOCBP) as defined in [Appendix 4](#), or

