7.2.1.1. Daprodustat Starting Dose

The starting dose of daprodustat will be assigned based on prior rhEPO or analog dose at randomization, Day 1 (Table 4).

Table 4 Daprodustat Starting Dose

[figure not shown]
RhEPO or Analog Dose at Randomization (Day 1)			Daprodustat Dose
Epoetins (including biosimilars) (U/week IV) ¹	Darbepoetin ($\mu\text{g}/4\text{week SC/IV}$) ²	Methoxy PEG-Epoetin beta ($\mu\text{g}/\text{month SC/IV}$) ^{3,4}	(mg, three-times weekly)
1500 to 2000	20 to 30	30 to 40	8
> 2000 to < 10000	>30 to 150	>40 to 180	12
$\geq 10,000$ to < 20000	>150 to 300	>180 to 360	16
$\geq 20,000$	>300	>360	24

PEG=polyethylene glycol

1. Standardized rhEPO IV dose (U/week) = $161/113 * (\text{epoetin SC dose (units)} / (\text{frequency}))$ [Beserab, 2002]
2. Conversion of 250 U:1 μg (epoetin IV:darbepoetin alfa) utilized and rounded to the nearest available dose strength [Stern, 2008]
3. Conversion of 1:1.2 μg (darbepoetin alfa:methoxy PEG-epoetin beta) utilized and rounded to the nearest available dose strength [Choi, 2013]
4. Conversion of 208 U:1 μg (epoetin IV: methoxy PEG-epoetin beta)

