7.2.2. Participants Randomized to Epoetin Alfa

Participants who are randomized to the epoetin alfa treatment arm will receive placebo tablets and epoetin alfa IV. A starting dose will be assigned for epoetin alfa as described in Section 7.2.2.1. A starting dose will be assigned for placebo, following the algorithm described for daprodustat in Table 4, and as shown in Table 5. Dose levels will be titrated for both the active and inactive study treatments, and new containers dispensed for each treatment with each change in dose.

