7.2.2.1. Epoetin Alfa Starting Dose

The starting dose(s) for participants receiving epoetin alfa are as follows:

- For participants with a Day 1 Hgb ≤ 11.0 g/dL:
 - For participants already on epoetin alfa the starting dose will be the same as their currently scheduled dose, rounded to the nearest available study treatment dose.
 - For participants receiving rhEPO analogs, the starting dose will be an IV epoetin alfa equivalent dose rounded to the nearest available study treatment dose. (Refer to Table 4 for conversion factors to determine equivalent epoetin alfa doses.)
- For participants with a Day 1 Hgb > 11.0 g/dL and ≤ 11.5 g/dL:
 - For participants already on epoetin alfa the starting dose of IV epoetin alfa will be reduced from their current scheduled dose, rounded to the nearest study treatment dose, to the next lower available dose with the aim of maintaining Hgb within the range of 10.0 to 11.0 g/dL.

- For participants receiving rhEPO analogs, the starting dose of IV epoetin alfa will be reduced from their current scheduled rhEPO analog equivalent dose, rounded to the nearest study treatment dose, to the next lower available dose of IV epoetin alfa with the aim of maintaining Hgb within the range of 10.0 to 11.0 g/dL. (Refer to [Table 4](#) for conversion factors to determine equivalent epoetin alfa doses.)

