10.3. Statistical Analyses

10.3.1. Efficacy Analyses

Endpoint	Statistical Analysis Methods
Primary	
Mean change in Hgb between baseline and EP (Weeks 28-52): The primary efficacy estimand is to compare the effect of treatment for the evaluation of mean change from baseline in Hgb during a 24-week evaluation period (Weeks 28 to 52 inclusive) in all ITT participants with at least one Hgb during the EP. The analysis will use an analysis of covariance (ANCOVA) model. For each participant, the baseline Hgb will be the value obtained on Day 1, prior to taking randomized treatment, and Hgb during EP will be determined by calculating the mean of all available Hgb values between Weeks 28 to 52 inclusive regardless of adherence to randomized treatment. The ANCOVA model will include randomization stratification factor, baseline hemoglobin, and treatment. It will provide a point estimate and two-sided 95% CI for the treatment effect, together with the one-sided non-inferiority test p-value. Non-inferiority will be established if the lower limit of the two-sided 95% CI is greater than the margin of -0.75 g/dL. There will be no imputation for missing data but imputation will be explored via sensitivity analyses
 
Sensitivity and Supplementary Analyses: Sensitivity analyses for the primary estimand will include a multiple imputation-based “tipping point” analysis where assumptions are adjusted until non-inferiority is lost by imputing data for participants who did not fully complete the EP. A further supplementary analysis will evaluate efficacy in those participants who adhere to randomized treatment, defined as ITT participants with at least one

Endpoint	Statistical Analysis Methods																														

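### The primary ANCOVA is valid but leaves out prior rhEPO dose, a collected baseline variable that might narrow the primary interval a little at small cost

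*SAP*

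**What the plan says.** The protocol and the SAP agree on the primary model. Protocol 10.3.1: "The ANCOVA model will include randomization stratification factor, baseline hemoglobin, and treatment". SAP 7.1.5.1: "The ANCOVA model used to quantify the difference in mean Hgb change will adjust for the following baseline values", followed by treatment, baseline Hgb and region as randomized.

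On predictors of response, protocol 5.5 reports from the Phase 2 modelling that "baseline Hgb, body-weight, and prior dose of rhEPO and its analogs were the most relevant covariates of Hgb response to daprodustat". It sets body weight aside for dosing purposes and carries prior dose forward.

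Prior dose is known before randomization. Inclusion criterion 2 requires "Use of any approved rhEPO or analog for at least 8 weeks prior to the screening visit and continuing during the screening period", and criterion 3 sets a minimum Day 1 dose. Dosing also depends on it. Protocol 7.2.1.1: "The starting dose of daprodustat will be assigned based on prior rhEPO or analog dose at randomization, Day 1". Protocol 7.2.2, for the control arm: "A starting dose will be assigned for placebo, following the algorithm described for daprodustat in Table 4". SAP 14.6.2.1 converts all prior ESA use to one continuous figure in U/week of IV epoetin.

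For the primary endpoint, SAP 5.4.2 uses this variable only as a subgroup split at 7,000 U/week, with a level for missing values, and as a component of the hyporesponder definition. Randomization is stratified by region alone (protocol 7.3).

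**The concern.** Of the three covariates the sponsor's own modelling singled out, only baseline Hgb is in the primary model. Prior dose marks resistance to rhEPO. If it still predicts Hgb in Weeks 28 to 52 once baseline Hgb and region are accounted for, that predictable variation stays in the residual, and the confidence interval compared with -0.75 g/dL may be somewhat wider than necessary. Because prior dose is not a stratification factor, the arms of 268 and 134 can also differ on it by chance. A separate subgroup display shows such a difference but does not adjust the primary estimate for it.

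Only precision is at stake. Leaving the term out neither biases the comparison nor raises the type I error.

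**Working it through.** **Inputs.** From protocol 10.1.1: SD 1.5 g/dL, true difference 0, margin -0.75 g/dL, 402 randomized 2:1 (268 and 134), about 10% without Hgb in the evaluation period, stated half-width 0.33 g/dL, least favourable passing estimate -0.42 g/dL. From protocol 10.1.2: power by SD and true difference. The share of variance explained by prior dose (R², or partial correlation ρ) is in neither document and is assumed throughout.

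**Reproducing the plan.** 268 × 0.9 ≈ 241 and 134 × 0.9 ≈ 121. SE = 1.5 × √(1/241 + 1/121) = 0.167. Half-width = t(0.975, 360) × 0.167 = 0.329, and -0.75 + 0.329 = -0.421. Both match the protocol. Power at a true difference of 0 is 99.4%, which matches the stated figure of above 99%.

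**Adding prior dose.** The half-width is multiplied by √(1 - R²). The equivalent number of extra evaluable participants is 362/(1 - R²) - 362.

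| Assumed R² | Half-width (g/dL) | Least favourable passing estimate (g/dL) | Equivalent extra n |
|---|---|---|---|
| 0% | 0.329 | -0.421 | 0 |
| 2% | 0.325 | -0.425 | 7 |
| 5% | 0.320 | -0.430 | 19 |
| 10% | 0.312 | -0.438 | 40 |

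**Power.** This uses the noncentral t with the protocol's rounded 360 evaluable (240 and 120) and noncentrality (0.75 + d)/SE, where d is the true difference and SE = 1.5 × √(1 - ρ²) × √(1/240 + 1/120). At ρ = 0 the SE is 0.1677, and at ρ = 0.3 it is 0.1600. For d = -0.3 the noncentrality therefore rises from 0.45/0.1677 = 2.68 to 0.45/0.1600 = 2.81.

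| Assumed ρ (R²) | Power, d = 0 | Power, d = -0.2 | Power, d = -0.3 |
|---|---|---|---|
| 0 (0%) | 99.4% | 90.5% | 76.3% |
| 0.1 (1%) | 99.4% | 90.8% | 76.7% |
| 0.2 (4%) | 99.5% | 91.6% | 78.0% |
| 0.3 (9%) | 99.7% | 92.9% | 80.1% |

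**Cost if the term explains nothing.** One lost degree of freedom widens the interval by about 0.1%.

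**Chance imbalance.** If half of participants took at least 7,000 U/week (assumed), the 95% range for the difference in that proportion between arms is ±1.96 × √(0.25 × (1/268 + 1/134)) = ±0.104, about 10 percentage points.

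**Limit of the sums.** The 1.5 g/dL comes from a two-sample t-test without covariates. If baseline Hgb and region already explain some variance, the residual SD is lower. The percentage reductions then still hold, but the gains in g/dL are smaller than shown.

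**The case against.** The strongest objection is that the design works against the association. The Phase 2 finding concerns response to daprodustat and was used to choose starting doses. It says nothing direct about mean Hgb at Weeks 28 to 52 in a treat-to-target trial with an epoetin arm. Both arms start from prior dose. For control participants with a Day 1 Hgb up to 11.0 g/dL, protocol 7.2.2.1 states: "For participants already on epoetin alfa the starting dose will be the same as their currently scheduled dose, rounded to the nearest available study treatment". Both arms are then titrated on Hgb for 28 weeks. Protocol 5.4 says of that stabilization period: "This period of time provides the best opportunity for participants to be titrated to their optimal dose of study treatment prior to the EP". Much of the effect of prior dose may be gone by Week 28.

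This stands, and it is why the gain cannot be asserted. It does not show that the gain is zero. Doses are capped (Tables 5 and 6), a rescue algorithm provides for inadequate response (7.9), protocol 5.4 expects some titration to continue in the evaluation period, and the SAP estimand keeps Hgb after discontinuation, rescue and transfusion. Resistance could still show in the endpoint.

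It is also fair to say that the protocol and SAP are consistent, that the primary endpoint will be examined by prior-dose and hyporesponder subgroups, and that body weight is omitted too. Protocol 5.5 found the weight effect unimportant for dosing, which makes prior dose the better candidate but is not itself a verdict on either as an ANCOVA term.

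**Conclusion.** A cheap improvement to a sound model. Over the assumed range of 0% to 10% of residual variance, the half-width falls by 0 to 0.017 g/dL against a margin of 0.75. At the planning assumptions power is above 99% with or without the term. The gain is visible only for a true difference near -0.3 g/dL, and there only towards the top of the assumed range.

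A reader might infer that the primary interval is definitely wider than it need be. The documents do not support that: they give no correlation of prior dose with evaluation-period Hgb, and the dosing design may have removed it. A reader might also infer that the omission biases the result or endangers the non-inferiority test. It does neither. Treatment is randomized, the stratification factor and baseline value are adjusted for, and the model is pre-specified. The point rests on the term costing almost nothing if useless and possibly helping if not.

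**What to change.** Before unblinding, amend SAP 7.1.5.1 as follows.

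- Add one pre-specified form of the covariate, log standardized prior ESA dose (U/week, SAP 14.6.2.1), to the primary ANCOVA and its supportive ANCOVAs.
- State a simple rule for missing values, for example the overall median taken without regard to arm, so that all randomized participants stay in. The rule should also cover a derived dose of zero, which has no logarithm.
- Put the same term in the monotone imputation regression, so that the imputation and analysis models agree, and say whether it stays when the SAP's fallback steps for sparse cells apply. The primary analysis now imputes missing Hgb for all randomized participants, so this matters more than it did under the protocol's plan.
- In the prior-dose subgroup model, say whether the continuous term is dropped, as SAP 5.4.2 already does for region in the country and US/non-US subgroups.
- Report the protocol's three-term model as a sensitivity analysis.

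The cost is one more model term, a few lines of programming on a variable already derived, and a documented departure from the protocol's primary model in SAP Table 1. Protocol 10.3.1 leaves room for further covariates in the analysis plan, and that table already records the move to multiple imputation.
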